4.10 Questionnaire Measures

4.10.1 Baseline measures

A baseline questionnaire will include questions regarding demographic information (including age, gender, profession, ethnicity, postcode (for purposes of identifying indices of multiple deprivation score)) current smoking status, previous use of SSS, ease of internet access, and motivation to guit, measured using the one item 'Motivation to Stop Scale', MTSS (Kotz et al., 2013) and a single item Likert scale (Hummel et al., 2017). Health-related quality of life data will be collected using the EQ5D-5L instrument to inform the health economic analysis, and the ICECAP-A (ICEpop CAPability measure for Adults) instrument will be used to measure general wellbeing. In addition, we have developed a bespoke resource use questionnaire to gain insight into the costs both to individuals and to the public purse of resources accessed as a result of participation in the study or use of the Stopapp (see appendix E). Participants will be given measures online via the project website. If they register but do not complete baseline measures within two weeks we will send email reminders. Those recruited through GP practices will be sent a reminder (using same method as initially used by GP surgery) two weeks after the first communication. All smokers who agree to take part in the study and return baseline guestionnaire responses will be randomised into either the intervention or control group as described above.

4.10.2 Two month follow-up

Follow up emails will be sent approximately two months after completion of the baseline questionnaire, to invite participation in the follow-up questionnaire. Emails containing a link to the follow-up measures will be sent to all participants to assess feasibility and acceptability of these, and likely attrition rates in a future trial. The questionnaire will also ask them to confirm whether they booked an appointment and attended a SSS, set a quit date and reached a 4-week abstinence, and explain what prompted them to book an appointment. Pinnacle Health Ltd will run a search of the PharmOutcomes and Outcomes4Health systems for our participants (where they consented to this) and provide us with their service use data to test feasibility of sourcing objective evidence of booking, attendance (and did not attends; DNAs), guit dates set, and CO tested 4 week guits. We will also assess feasibility and acceptability of follow-up measures of; motivation using the MTSS and a single item Likert scale (Hummel et al., 2017); the EQ5D-5L instrument; the ICECAP-A instrument and a resource use questionnaire to capture participant use of NHS and other resources for both intervention and control arms. Non-responders to the email will be contacted two weeks later with a reminder to respond. We will send an email with a link to the information leaflet provided to the control group, to anyone who contacts us after the end of the period of recruitment to the study until the end of December 2019.

4.10.3 Data on costs associated with delivering the intervention versus usual care

We will gather, through trial processes, data on the costs associated with delivering the intervention (e.g. web hosting, text messages and usual care (e.g. telephone calls taken to book in appointments). We will also collect data on costs and resource use associated with promoting the intervention and usual care (e.g marketing through social media, posters on buses etc.). Costs and resource use associated with attendance or non-attendance (Did not attend, DNA rates) at SSSs will also be collected from PharmOutcomes or Outcomes4Health system).

B – Nested qualitative process evaluation

Procedure for participant interviews

At baseline, following randomisation, we will ask all participants (using a single yes/no question) if they are interested in participating in a brief follow-up telephone interview at the end of the study, regardless of whether or not they end up completing the study. For all participants that indicate an interest, we will request a contact telephone number and their consent to process this information in addition to personal data already collected. For participants providing this consent, we will create a new Excel database (process evaluation contact database) containing: their unique ID, setting recruited from (GP, community or online), experimental condition allocation, and their responses to a number of demographic questions asked at baseline for the purposes of randomisation i.e. gender, self-report socio-economic status. This database will be stored on the research lead's private password protected OneDrive folder (located on CU server). At the end of data collection (30th June) we will also record in this database, study retention information for each participant (i.e. whether they completed the study or dropped out at baseline or intervention phase) and whether they accessed Stop Smoking Services (using PharmOutcomes/Outcomes for Health data – see above). Using this data, we will select approximately 30 feasibility RCT participants and invite them to participate in the process evaluation interviews.

In order to ensure a good representation from more disadvantaged smokers in particular, we will apply maximum variation sampling and seek to over represent where possible, smokers from lower socio-economic groups, whose voices are not typically included in this type of research (on basis of data stored within this database as listed here). NB the above database will be retained until the end of data processing (data analysed and findings reported) after which point it will be deleted.

Invitation will be by telephone and those who wish to participate will be sent a followup email directing them to a new study page on eNgage (set up specifically for the process evaluation interviews). Here participants can read and download the participant information details and review the consent statements. Participants will be required to endorse all consent statements to activate the 'join project' button. On clicking 'join project', they will receive a message telling them that they will be contacted by a member of the research team to set up a mutually convenient time for the interview. The interviews will last approximately 30 minutes, and will be audio recorded using telephone interview recording devices. Interview transcripts will be transcribed verbatim in preparation for analysis. Participants will be able to withdraw their consent for up to 2 weeks after participation in the interview. Please refer to appendix H for a copy of the interview schedule. We will allow data analysis to determine saturation point and when to stop, but anticipate conducting up to 30 interviews. We will explore acceptability and user experience in line with each of the identified research objectives.

Procedure for staff interviews within recruitment settings

In addition, we will invite a range of staff from recruitment settings to also comment on acceptability and experience of supporting the trial (see appendix I). The staff contacts made at recruitment sites during data collection will be invited to participate in process evaluation interviews. As above, a separate project page on eNgage will be set up for this purpose. Here participants can read the Participant Information Sheet and will be asked to provide consent. All remaining procedure as for trial participants described above. Data analysis will determine saturation point but we will aim to recruit around 3 members of staff from each setting type (GP, community, online).

All qualitative data will be subject to thematic analysis using Nvivo software.

Procedure for data management

All interviews will be digitally recorded. Once each recording is complete, it will be downloaded on to the shared password protected project folder and named according to the participants' unique ID. The original recording on the recording device will then be deleted. Audio files will then be transcribed by a CU approved transcription service with whom we have a data sharing agreement in place. Identifying data such as names will be removed from transcriptions to ensure anonymity of participants. Once the research team is satisfied that all transcriptions are complete, the audio files will be deleted.

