3.3 Secondary Objectives

Secondary objectives of the feasibility trial are to estimate the:

- **3.3.1** acceptability of randomisation and the StopApp intervention for participants
- **3.3.2** acceptability of primary and secondary outcome measures and measures required for cost-effectiveness and cost utility analyses in a future trial
- **3.3.3** key costs which would be incurred in delivering the intervention and usual care, including a comparison of non-attendance at SSS (Did-not-attend or DNA rates) between each arm of the trial.
- **3.3.4** feasibility of accessing SSS and GP data (if recruited via GP) on attendance, quit dates set and four-week quits for trial participants
- **3.3.5** any differential recruitment and attrition rates across socio-economic groups and age and gender
- **3.3.6** rate of SSS attendance in the treatment and control groups to estimate the event rate of the primary outcome measure for a future trial and support future trial sample size calculations

4. Methodology

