4.8 Intervention access

Following randomisation, both groups will be sent an email with near identical content, asking participants to either follow a web-link to read an information leaflet about SSS (control group) or follow a web-link to the StopApp (intervention group). A reminder email will be sent to all participants two weeks later. Please see procedure below for further information on when access to these materials is provided. Participants in both conditions will be told that if they wish to book an appointment at the SSS, then they are free to do so, but in taking part are under no obligation to do so. Acceptability of randomisation and the intervention will be assessed by follow-up qualitative interviews with a sub-sample of participants (see nested qualitative process evaluation below for further information on these interviews).

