4.9.1 Procedure for participants

Please refer to Figure 1 for flow diagram illustrating participants' route through the project. Eligible smokers will be recruited from one of three settings (described above in section 4.3) and provided with a link and/or QR code to the study webpage. The study webpage is delivered via secure bespoke study management software known as 'eNgage' which is hosted on Coventry University servers (see below for information on eNgage) [https://engage.coventry.ac.uk].

Participants will be required to endorse mandatory consent statements (time/date stamped and version of participant information sheet recorded) before being able to participate. Informed consent will be obtained online in accordance with the updated General Data Protection Regulation (GDPR) guidelines.

Following consent, participants will be guided through the process of completing guestionnaires and accessing the intervention/control materials (see procedure for data management below for further detail on how this will happen). They will be asked to complete a baseline questionnaire (appendix E) which will take approximately 20 minutes to complete. They will then be randomised to either the intervention group, and then directed to the StopApp, or the control group, and then directed to the online pdf leaflet. Participants in both groups will have continued access to the content of either the intervention or the control materials (although they have been designed to be used as a one off). Two months later all participants will be asked via email to complete an online follow-up questionnaire (appendix E). Participants will also be asked if they are interested in taking part in telephone interviews to investigate the acceptability of MyWay (by endorsing a box at end of the baseline questionnaire). Consenting participants will complete one telephone interview after follow-up. Staff from recruitment settings (community and GP) will also be invited to participate in telephone interviews about their involvement in the study. See procedure for nested qualitative process evaluation below for further details (Part B; page 21).

Figure 1: Flow diagram illustrating participant's route through project.

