On 'joining' a project, eNgage directs participants to Qualtrics to complete baseline measures. The participant's email address is transmitted by eNgage to Qualtrics to enable auto-scheduled email invitations and reminders to be sent throughout the project at relevant time points (i.e. completion of questionnaire and access to intervention). Each participant's unique ID is also transmitted to enable all data collected within eNgage and Qualtrics to be linked (e.g. provision of consent and questionnaire responses).

The randomisation of participants to experimental conditions occurs within eNgage. After each participant has completed their baseline questionnaire within Qualtrics, eNgage will assign condition. Whilst assignment is random, the algorithm applied uses minimisation to ensure balance by factors that are likely to affect SSS access (gender, self-report socio-economic status). Data with respect to these factors is collected for each participant within the baseline questionnaire. On study set-up within eNgage, the research team specify what these factors are and their location within the baseline questionnaire (e.g. Qs1-4). eNgage retrieves this data from Qualtrics and uses it to nominate assignment. eNgage uses the participant's unique ID (sent to Qualtrics previously) to identify the individual. Each participant's response to these questions and condition assignment is additionally stored within eNgage to enable auditing of this process.

Following assignment, participants are directed to the respective intervention or control materials (both stored on the CU server). Analytics data on their use of these materials is collected by Matomo (see below). Following this, participants are directed to complete the follow-up questionnaire within Qualtrics, at 2-months after baseline.

NB. for the My Way study, there will be a number of identical eNgage project pages, one for each of the different recruitment settings. The purpose of this is to enable the unique ID created for each participant to be associated with the type of setting they were recruited from. This is necessary to assess the success of our recruitment strategy across the different settings. The URL for each page will be the only thing that is different for each project page and this will be provided accordingly for those recruited within each of the settings.

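### Interview opt-in comes too late to reach people who join but abandon the baseline questionnaire, so the interviews cannot explore why they leave

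*Protocol*

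**What the plan says.** Two places set the moment at which participants are asked about an interview. Section 4.9.1 has them indicate interest "by endorsing a box at end of the baseline questionnaire". Part B, the nested qualitative process evaluation, places the question after allocation: "At baseline, following randomisation, we will ask all participants (using a single yes/no question) if they are interested". Part B adds that the question is put whether or not the person goes on to complete the study.

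Those who say yes, supply a telephone number and consent to its use are entered in a contact database with unique ID, recruitment setting, allocated condition, gender and self-reported socio-economic status. At the end of data collection the team adds whether each person used stop smoking services, and retention status: "whether they completed the study or dropped out at baseline or intervention phase". About 30 participants are then selected from this database by maximum variation sampling, with lower socio-economic groups over-represented where possible, and are invited by telephone.

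The interviews serve secondary objective 3.3.1, "acceptability of randomisation and the StopApp intervention for participants". Section 4.8 gives the method: "Acceptability of randomisation and the intervention will be assessed by follow-up qualitative interviews with a sub-sample of participants". For the measures, section 4.12 uses level of completeness as well as interviews.

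**The concern.** Attrition at baseline is part of the primary objective (section 3.2), and section 6 uses data on those lost through attrition to judge the health equity of the method. A feasibility trial needs the reasons for early loss as well as the count, because the reasons show what to change before a definitive trial. Part B evidently wants to hear from people who do not finish. If the opt-in sits behind a questionnaire of about 20 minutes, the first group lost after consent cannot be heard. The aim of including disadvantaged smokers, whose voices are usually missing, is then confined to those who got through the questionnaire. This cannot be repaired afterwards, because neither a telephone number nor agreement to be approached for interview would have been collected from the people concerned.

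**Working it through.** The main question is one of sequence, so the sections are set side by side.

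1. **Order of events.** Sections 4.9.1 and 4.9.2 give consent and joining on eNgage, then the baseline questionnaire in Qualtrics, then randomisation, then the materials. Section 4.9.2: "After each participant has completed their baseline questionnaire within Qualtrics, eNgage will assign condition". Section 4.10.1 agrees: those who take part and "return baseline guestionnaire responses will be randomised into either the intervention or control group".
2. **Opt-in under section 4.9.1.** The box is at the end of the questionnaire. A person who stops part-way does not reach it.
3. **Opt-in under Part B.** The question follows randomisation, which follows baseline completion. A person who stops part-way does not reach it here either.
4. **Sampling frame.** Entry to the contact database needs a yes, a telephone number and consent. One of its fields is allocated condition, which presupposes randomisation. No other frame for participant interviews is given.
5. **People who register but do not finish baseline.** Section 4.10.1 provides email reminders and no interview question.
6. **Result.** The number of interview candidates who abandoned baseline is zero by design, whichever opt-in point is meant.
7. **Retention category.** Sections 3.2 and 4.12 name three stages of attrition: baseline, intervention (or control) access, and two-month follow-up. In those terms, loss at baseline means not completing baseline, and nobody of that kind is in the database. The category would be empty.

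**Illustration of size.** The protocol gives no expected loss between joining and completing baseline, so 10% to 30% is assumed. For N randomised and a loss proportion p among joiners, the number lost is N/(1 − p) − N.

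- N = 162, p = 0.10: 162/0.90 − 162 = 180 − 162 = 18.
- N = 162, p = 0.30: 162/0.70 − 162 = 231.4 − 162 ≈ 69.

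If 162 is instead the number who join, the loss is 162 × 0.10 ≈ 16 to 162 × 0.30 ≈ 49. The point does not depend on either range.

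**The case against.** The strongest reply is that early drop-outs are not ignored. Section 4.12 reports attrition at baseline by setting, assesses completeness and runs a missing-value analysis. Section 4.9.2 uses web analytics to find where people leave. Staff at recruitment settings are interviewed too. A reader might infer that the baseline measures are judged only by people who accepted them. The documents do not support that, and this part of the reply stands. What these sources lack is the drop-outs' own reasons.

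A reader might also infer that acceptability of randomisation is judged only by people content with it. That does not follow. Someone who abandons baseline has already consented and was never allocated, so has not refused an allocation. Someone allocated and then disengaged, perhaps because of the arm received, can still be interviewed if they opted in. People opposed to randomisation would be expected to decline at consent, and no opt-in placed after joining would reach them.

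Finally, a reader might conclude that sampling people who dropped out at baseline is impossible. That depends on an undefined term. Part B lists only two drop-out categories, which would fit coding by the last stage completed: baseline done but materials not opened, or materials opened but follow-up not done. On that reading both categories can be filled. The stage names in sections 3.2 and 4.12 point the other way, so the term needs a definition. Under either reading, those who abandoned the questionnaire remain outside the frame.

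Nor is there a basis for predicting that the interviews will find the questionnaire acceptable. People who completed it can still criticise it.

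**Conclusion.** The point holds in a limited form. Sections 4.9.1 and Part B disagree on whether the opt-in comes before or after randomisation and must be reconciled. Under either timing, all of those who join and then abandon baseline are outside the interview frame, so their reasons cannot be explored by interview. This rests only on the sequence stated in the protocol and on the contact database being the sole frame. The drop-out category in Part B is undefined, and would be empty on the stage names used elsewhere. The quantitative estimates of recruitment and attrition are unaffected. The range of 18 to 69 people rests on an assumed 10% to 30% loss and is illustrative only. The change is worth making before recruitment because the missing information cannot be recovered later.

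**What to change.** - Offer the interview-interest question and telephone number as an optional consent item when joining on eNgage. Section 4.9.2 already lists responses to optional consent questions among the data that eNgage keeps.
- Align section 4.9.1 and Part B to that single point, and remove the later question.
- Define what dropping out at baseline means, using the stages in sections 3.2 and 4.12.
- Keep some of the approximately 30 interviews for people who joined but did not complete baseline.
- State that acceptability of randomisation is assessed only among those allocated, and not among people who declined to join.

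**Cost.** One more optional item at joining, with a telephone number requested before any study activity, and rewording of two sections; the number of interviews does not change. For baseline drop-outs little beyond recruitment setting may be known, so over-representation by socio-economic status may not be applicable to them. Whether people who left a questionnaire would agree to a 30-minute interview is unknown.

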4.10.4 Measurement of potential harms

As this is a behavioural intervention with extremely limited potential for harm or adverse events we do not consider it necessary to measure these.

4.11 Estimated recruitment rate and proposed sample size

The primary objective of this study is to assess the feasibility of recruitment to a potential future definitive RCT and therefore formal power analysis is not appropriate. However, in order to determine the target sample size we have drawn on two sources. Teare et al. (2014) recommend that external pilot and feasibility studies with binary outcome measures (in this case attend vs. does not attend SSS) recruit at least 60 participants in each group (minimum N=120) and a maximum of 100 participants in each group (maximum N=200). In addition, our sample size calculations, based on similar definitive RCT data about recruiting smokers to trials via letters from their GPs, suggested that we would need to enrol 980 smokers to detect a 7% difference between control and intervention arms in a definitive trial. Based on this estimate, any trial would need to recruit 1.8 participants per day to achieve the required recruitment in 18 months. We plan to recruit for three months, and based on needing to recruit 1.8 participants per day, we need to reach a required sample size of **162** participants (54 per setting). With a sample size of 162, the recruitment rate of smokers for a full RCT will be estimable with a precision (95% CI width) of +/- 5%.

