4.12 Statistical analysis plan

Feasibility and acceptability of all measures will be assessed by level of completeness and by follow-up qualitative interviews with a sub-sample of participants (see detail above on nested qualitative study). We will calculate recruitment rate via GP surgeries as a percentage of those recruited from those smokers identified on participating GPs lists. We will calculate recruitment via community and online settings as the time taken and spend required to recruit 54 participants and/or the number recruited and spend over three months. We will

calculate the average recruitment rate per day across the three settings. We will provide percentage rates for attrition across each recruitment setting at each of baseline, intervention/control access, and two-month follow-up.

We will look at the observed difference between intervention and control groups for bookings and attendance at SSS and use this data to support estimates for the required sample size for a definitive trial. Clinical significance will also be used in these estimates and a comparison of the two will help to determine future trial feasibility. We will assess level of completeness of all measures and run missing value analysis to determine whether any missing data are missing at random or whether patterns of missing data may indicate a problem with measures.

We will report observed and self-reported bookings, attendances, quit rates set and four-week quits across the intervention and control groups, and the proportion of participants agreeing to allow access to SSS and GP data (where relevant) relating to smoking status and SSS attendance.

We will report on numbers of higher versus lower SES status participants recruited as well as age and gender, and assess using chi-squared analysis whether SES status, age or gender are associated with attrition at baseline, intervention/control access and two-month follow-up.

5. Ethical Considerations

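### The ±5% precision stated for the recruitment rate has no defined rate or denominator, cannot be reproduced, and does not hold for the per-day rate used for stop/go

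*Protocol*

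**What the plan says.** Protocol section 4.11 starts from a definitive trial in which "we would need to enrol 980 smokers to detect a 7% difference between control and intervention arms", and concludes that "any trial would need to recruit 1.8 participants per day to achieve the required recruitment in 18 months". Three months at that rate gives the target of 162, or 54 in each of three settings. For that target it then claims: "the recruitment rate of smokers for a full RCT will be estimable with a precision (95% CI width) of +/- 5" per cent. No formula, assumed proportion or denominator is given, and a half-width is labelled a width.

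Section 4.12 defines recruitment in three ways:
- GP surgeries: "We will calculate recruitment rate via GP surgeries as a percentage of those recruited from those smokers identified on participating GPs lists".
- Community and online: time and money needed to reach 54, and/or the number recruited and the spend over three months. Neither is a proportion.
- Overall: "calculate the average recruitment rate per day across the three settings".

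Section 6 judges the feasibility of a future trial against an average of at least 1.8 recruits per day, and on whether one or more settings can supply the numbers. On attrition, section 4.12 says "We will provide percentage rates for attrition across each recruitment setting at each of baseline, intervention/control access, and two-month follow-up", with no precision attached.

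**The concern.** Estimating recruitment is half of the primary objective (section 3.2), and the ±5% sentence is the only statement of how precisely 162 participants will do it. But 162 is the number recruited. That makes it the numerator of a recruitment rate, or a count over time; it is not the number of people approached. If the 5% cannot be tied to any rate that section 4.12 reports, the reader has no valid precision for the quantity behind the progression decision. Someone who takes the figure at face value would treat an observed 1.8 per day as nearly settled, when the data would also be compatible with a definitive trial that overruns its 18 months by about three.

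**Working it through.** **Inputs.** From section 4.11: N = 162, 54 per setting, three months of recruitment, 980 for the definitive trial, 1.8 per day, 18 months, ±5% at 95% confidence. From section 4.12: the three recruitment measures. From section 6: the threshold of 1.8 per day. Months are taken as 30 days, which reproduces the protocol's own figures.

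**1. The target reproduces.** 980 / (18 × 30) = 1.81 per day; 1.8 × 90 = 162; 162 / 3 = 54.

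**2. The ±5% does not.** Take 162 as a binomial denominator, with half-width 1.96 × √(p(1−p)/162):

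| p | half-width (points) |
|---|---|
| 10% | 4.6 |
| 12% | 5.0 |
| 20% | 6.2 |
| 30% | 7.1 |
| 50% | 7.7 |

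Setting the half-width to 5 points gives p ≈ 12% or, by symmetry, 88%. Neither appears in the protocol. Other readings do no better:
- Wilson intervals also put the crossing at about 12%.
- A total width of 5 points needs p ≈ 2.7%.
- At p = 50%, ±5 points is an 80% interval (5.03), not a 95% one.
- With n = 54, ±5 points needs p ≈ 3.6%.

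**3. Recruits per day, overall.** Exact Poisson limits for a count x are χ²(0.025; 2x)/2 and χ²(0.975; 2x+2)/2. For x = 162 they are 138.0 and 189.0. Divided by 90 days, the rate is 1.80 per day, CI 1.53 to 2.10, that is −15%/+17%. The approximation 1.96/√162 = 15.4% agrees. A relative ±5% would need (1.96/0.05)² ≈ 1,537 recruits.

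Time to enrol 980:
- at 2.10 per day, 980/2.10 = 467 days, or 15.6 months;
- at 1.533 per day, 980/1.533 = 639 days, or 21.3 months.

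A true ±5% (1.71 to 1.89 per day) would have implied 980/1.89 = 519 days to 980/1.71 = 573 days, or 17.3 to 19.1 months.

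**4. Recruits per day, one setting.** For x = 54 the limits are 40.6 and 70.5. Divided by 90, the rate is 0.60 per day, CI 0.45 to 0.78 (−25%/+30%).

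**5. GP percentage.** The denominator is the number of listed smokers, L, which the protocol does not give. With 54 recruits, p = 54/L and the half-width is 1.96 × √(p(1−p)/L). Over an assumed range of L:

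| L (assumed) | uptake | half-width (points) |
|---|---|---|
| 250 | 21.6% | 5.1 |
| 300 | 18.0% | 4.3 |
| 500 | 10.8% | 2.7 |
| 1,000 | 5.4% | 1.4 |
| 2,000 | 2.7% | 0.7 |

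The half-width falls below 5 points once L is about 256 or more. The relative error is still about 24% to 26% over L = 250 to 2,000.

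**The case against.** The strongest defence is that the sentence decides nothing. The 162 comes from 1.8 per day over three months, and at 81 per arm it also lies within the 60 to 100 per group recommendation cited in section 4.11. Stop/go compares an observed average with 1.8; no confidence limit and no ±5% enters that rule. This stands: neither the sample size nor the stop/go threshold is undermined.

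It is also fair to say that one recruitment rate may well meet ±5 points. The GP percentage does so once the lists hold about 256 smokers. So a reader who infers that the figure fails for every recruitment rate goes too far. But where it succeeds, that is owed to the list size and not to 162, so it does not support the sentence.

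Two other inferences should be resisted. One is that the protocol also presents attrition as known to ±5%. It does not: section 4.11 attaches the figure to recruitment alone, and section 4.12 gives no precision and no expected rate for attrition. The other is that the authors used 162 as a binomial denominator. That is a guess, since no method is shown; what can be said is that the rate and its denominator are undefined.

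Finally, precision is often left to a statistical analysis plan. Here, though, the protocol states a figure, and the figure does not fit the measures it goes on to define.

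**Conclusion.** Wrong as written. The ±5% has no defined rate or denominator, does not follow from the protocol's inputs, and does not describe the per-day rate used for stop/go. On the planned numbers that rate carries −15%/+17% overall and −25%/+30% in a single setting.

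This rests on the target being met exactly (162 in 90 days, 54 per setting) and on independent arrivals at a constant rate. Clustering by practice, site or campaign would widen the intervals.

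A single multiple of how far the 5% is out should not be quoted. The protocol does not say whether 5% is absolute or relative, and the answer differs between percentage points and relative error.

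**What to change.** Replace the precision sentence in section 4.11 with the expected precision of the recruitment measures in section 4.12:
- Overall daily rate: 1.8 per day, 95% CI about 1.53 to 2.10 if 162 are recruited in 90 days.
- Per-setting daily rate: 0.60 per day, 95% CI about 0.45 to 0.78 if 54 are recruited in 90 days.
- GP percentage: a binomial 95% CI with the number of listed smokers as denominator, giving the expected list size or a range for it.
- A note that the daily-rate intervals assume independent arrivals.

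A precision for attrition is optional, as none is claimed now. If one is added, the worst case (p = 50%) is ±7.7 points overall (n = 162) and ±13.3 points per setting (n = 54).

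This is a change of wording only. Sample size and conduct stay as they are; the cost is a less favourable stated figure.
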